8.4.1 ANALYSIS OF THE SECONDARY ENDPOINT(S)

Management of HTN within 6 months of meeting criteria will be described, including lifestyle counseling, dietitian referrals, subspecialty referrals, initiation of antihypertensive medications, and diagnostic imaging as individual endpoints in separate analyses and following the analytic approach described above for H3. Heterogeneity of the effects of the two implementation strategies will be examined in pre-specified subgroups defined by age (6-12, 13-17), BMI (>30 vs. <30), sex, and race/ethnicity, as feasible. Models described earlier will incorporate interaction terms of patient factors and study arm fixed effects and utilize study arm contrasts to estimate parameter estimates and standard errors for differences in implementation strategies within these subgroups of patients. We anticipate at least 60% response rate among 214 providers in completing the provider survey. We predict that one or more follow-up BPs within 12 months of meeting criteria for HTN will be available for 70% of patients meeting criteria for HTN at intervention clinics and 50% of patients meeting criteria for HTN at usual care clinics.

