5 STUDY POPULATION

In this study, we aim to evaluate the PedsBP CDS in up to 45 primary care clinics with an estimated total of 216 primary care providers and 360 rooming staff. The majority of sites are staffed by family practice physicians (n=31). Pediatricians (n=2), both family practice and pediatricians (n=4) or advanced practice providers alone (n=8) cover the remaining sites.

Based on prep data, we estimate that over the 18-month study period there will be 44,061 unique patients 6-17 years with BP, height and weight recorded, with an average of 2.02 visits per patient over the study period. Similar to demographics of the region, the population is 90% white, non-Hispanic. Fifteen percent of youth receiving care at these sites are obese, with BMI $\geq 95^{\text{th}}$ percentile. Elevated BP is common (10-20% of patients with at least 1 BP meeting

criteria for elevated BP), yet diagnoses for hypertension were only found in 120 (<0.3%).

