Figure 3. Example of Peds & TeenBP CDS for 6-year old meeting criteria for Stage 1 HTN

In the third component, the CDS will use the lowest SBP for that visit to assign BP percentiles and classify BPs as normotensive, elevated BP, stage 1 HTN, or stage 2 HTN. If the initial elevated BP is not repeated, the BP percentile will be calculated for the available measurements. BP percentiles are calculated as in Appendix B of the Fourth Report³⁶ and include the new reference population, as described in the 2017 Guidelines.⁹

In the fourth component of the CDS, for patients with BP $\geq 95^{\text{th}}$ percentile (6-12 years of age) or $\geq 130/80$ mmHg (13-17 years of age), the CDS reviews data pulled from the EHR including prior HTN diagnoses, prior BPs and heights. The index and previous BPs and diagnosis data are used to categorize elevated BPs as incident or persistent, and to determine whether a patient meets clinical criteria for new onset stage 1 or stage 2 HTN, or pre-existing HTN.

In the fifth component of the CDS, current medications (e.g., oral steroids or stimulants that increase BP or diuretics that lower BP) and prior diagnoses that may affect BP are displayed. In addition, current body mass index (BMI) and BMI percentile are calculated. For patients meeting criteria for obesity, BMI $\geq 95^{\text{th}}$ percentile with new onset HTN, obesity is noted in the CDS as a potential cause for the HTN.

In the sixth component of the CDS, providers receive tailored CDS for BPs $\geq 95^{\text{th}}$ percentile or $\geq 130/80$ mmHg. The CDS recommendations are specific, based on the magnitude of BP elevation (stage 1 or stage 2 HTN) and whether the BP is

incident or persistent. If the patient has a prior diagnosis of HTN, the CDS provides tailored feedback regarding whether the BP is at goal (<95th percentile) or elevated and possibly requires initiation or a change in medication.

In the seventh component of the CDS, current and previous SBPs and DBPs, within the last 2 years are graphed and displayed, with elevated BP, stage 1, and stage 2 HTN BP cutoffs specified. This feature allows providers to visualize patient-level variability and trends in BP over time. In addition, the CDS can be printed for families, to assist with shared decision making. An example, including the display of BPs over time, is shown in Figure 3.

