8.2 SAMPLE SIZE DETERMINATION

Aim 1. Preliminary data from EH indicate there were 44,061 unique patients age 6-17 with visits to the 45 largest EH primary care clinics in an 18-month period. This data also indicates that 16% (n=7,258) of patients age 6-17 years had an elevated BP at initial measurement and BP re-measurement occurred at 30% (n=2210) of encounters with an elevated BP. The initial PedsBP trial had a clinic-level ICC for BP re-measurement of 0.03 and BP re-measurement of 28% in UC and 47% in the PedsBP arm.²³ With an expected 7,258 patients (161 per clinic), this study has 99% power for the H1 comparison of low- plus high-intensity clinics (30 clinics) with 15 UC clinics (alpha=.05, two-sided test, ICC=0.03) to detect a raw BP re-measurement difference of 15% between the usual care arm (30%) vs. low- plus high-intensity arms (45%). The minimum detectable difference with 80% power is 8% (30% UC vs. 38% low- plus high-intensity arms). With an expected 4,840 patients (161 per clinic), this study has 80% power for the H2 comparison of low-intensity (15 clinics, 2420 patients) vs. high-intensity clinics (15 clinics, 2420 patients), with alpha=.05, two-sided tests, ICC=0.03, to

detect a minimum detectable difference in BP re-measurement of 10% between the low-intensity arm (40%) vs. the high-intensity arm (50%).

Aim 2. Based on the prior Peds & TeenBP trial²⁴, along with observational studies of pediatric HTN¹⁰⁻¹² we anticipate 2% of patients age 6-12 and 3% of patients age 13-17 will newly meet HTN criteria at a visit over 18 months, yielding a sample size of 1060 patients (24/clinic). The PedsBP study found that 21% of patients newly meeting HTN criteria were recognized over 6 months in UC and 55% in the PedsBP arm²⁴, and the clinic-level ICC for HTN recognition was 0.035. With 1060 patients (24/clinic) and 45 clinics, this study has 99% power (alpha=.05, two-sided test, ICC=0.035) for H3 to detect a difference in HTN recognition of 17% between UC (20%) and the low- plus high- intensity arms (37%), and a minimum detectable difference of 11% (20% UC vs. 31% low- plus high-intensity arms) at 80% power. For H4 the minimum detectable difference at 80% power for HTN recognition among 706 patients (24/clinic) is 14% between low-intensity (30%) and high-intensity (44%) arms. Power computations account for the design effect due to clinic randomization and unequal counts of clinics in some comparisons and were conducted with PASS 2019.

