The dependent variable for Aim 1 (BP_Remeasure) is a binary indicator of post-implementation re-measurement of BP at the index visit at which the elevated BP occurred. For H1 this endpoint will be predicted by a fixed effect study arm term (TeenBP_j) contrasting low- plus high-intensity PedsBP clinics with usual care clinics, stratification factors used in the clinic randomization (StratFactors_j), and patient-level covariates of age, sex, and SBP percentile of the elevated BP. A random intercept for clinics is included (u_{j0}) to account for the clinic-level randomization. The analysis for H2 will contrast high- and low-intensity clinics (HighVsLow_j) and exclude usual care clinics from the analysis, but otherwise be similar to H1. Statistically significant study arm contrasts (alpha=.05) and parameters in the expected direction will support the H1 and H2 predictions stated for Aim 1.

Hypotheses 3 and 4 for **Aim 2** posit that patients who newly meet HTN criteria at clinics with low- or high-intensity PedsBP CDS will be more likely to have their HTN recognized within 6 months as compared to patients seen at usual care clinics, and that recognition of HTN will be more likely for patients seen at high-intensity rather than low-intensity clinics. Generalized linear mixed-model regression with a logit link and binomial error distribution may be used to test the effect of the interventions following the same analytic strategy and equations for H1 and H3 above, with the substitution of HTN recognition as an endpoint in place of BP re-measurement, and the use of patient-level covariates of the lowest SBP percentile at the index visit, and BMI percentile at the index visit. Study arm contrasts will test differences in BP recognition for CDS (low-intensity or high-intensity) vs. Usual care and high-intensity vs. low-intensity. Statistically significant study arm contrasts (alpha=.05) and parameters in the expected direction will support the H3 and H4 predictions stated for Aim 2.

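### The BMI subgroup for effect heterogeneity uses one absolute cut at 30 for ages 6 to 17, so it is not the group the protocol defines as obese

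*Combined protocol and SAP*

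**What the plan says.** Section 8.4.1 states the aim of the subgroup work: "Heterogeneity of the effects of the two implementation strategies will be examined". The subgroups are "pre-specified subgroups defined by age (6-12, 13-17), BMI (>30 vs. <30), sex, and race/ethnicity, as feasible". On method it says: "Models described earlier will incorporate interaction terms of patient factors and study arm fixed effects". It gives no unit for BMI, no percentile label and no reason for choosing 30.

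Other sections describe weight status by percentile:

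- Section 5: "Fifteen percent of youth receiving care at these sites are obese, with BMI" at or above the 95th percentile.
- Section 6.1.1, fifth CDS component: "current body mass index (BMI) and BMI percentile are calculated", so the two are separate variables. For patients at or above the 95th percentile with new-onset hypertension, "obesity is noted in the CDS as a potential cause for the HTN".
- Section 8.4, Aim 2 model: "the use of patient-level covariates of the lowest SBP percentile at the index visit, and BMI percentile at the index visit".

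**The concern.** The subgroup analysis asks whether the high- and low-intensity strategies work differently by weight status. For children and adolescents the protocol ties obesity to a percentile, then forms the subgroup on a different scale without explanation. A reader who takes the group above 30 to be the obese youth described in section 5 would be reading a result about other patients.

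Age is a separate subgroup in the same sentence, and a fixed BMI value is not referenced to age. If older patients are more likely to exceed 30, a BMI-by-arm difference could partly be an age-by-arm difference. Section 8.4.1 does not say whether the two interactions are fitted together. Section 8.4 lists age as a covariate for Aim 1, but for Aim 2 names only the SBP and BMI percentiles, so it is unclear whether age stays in the Aim 2 model.

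**Working it through.** **Is 30 an absolute BMI?** Section 6.1.1 lists BMI and BMI percentile as two quantities, and section 8.4.1 writes BMI alone, so 30 reads as an absolute value. Reading it as a percentile would not help: a cut at the 30th percentile is not a cut at the 95th.

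**Do the groups match?** Obese under sections 5 and 6.1.1 means percentile of 95 or more. The 8.4.1 group is BMI above 30. A patient with percentile of 95 or more and BMI below 30 is obese by the first rule and in the lower group by the second. A BMI of exactly 30 is in neither group. The number of such patients cannot be computed, because no BMI distribution is given.

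**Plan figures.** Section 8.4.1 states no size or power for the BMI subgroup, so there is no figure to reproduce. For context, the base for comparing the strategies on Aim 2 is in section 8.2: "For H4 the minimum detectable difference at 80% power for HTN recognition among 706 patients (24/clinic) is 14" percentage points. With 1,060/45 = 23.56 patients per clinic and ICC 0.035, the design effect is 1 + 22.56 × 0.035 = 1.79. The effective size per arm is 15 × 23.56/1.79 = 197. For 30% versus 44% this gives power of 0.80 (t, 28 df) to 0.83 (z), in line with the stated 80%. BMI does not enter this calculation.

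**Age mix of the Aim 2 cohort.** Section 8.2 expects 2% of ages 6-12 and 3% of ages 13-17 to meet criteria, 1,060 in all from 44,061 patients. Let x be the number aged 6-12:

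0.02x + 0.03(44,061 − x) = 1,060, so x = 26,183, leaving 17,878 aged 13-17.

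The Aim 2 cohort is then 0.02 × 26,183 = 524 aged 6-12 (49.4%) and 0.03 × 17,878 = 536 aged 13-17 (50.6%). Of the 706 in the strategy comparison, about 349 are aged 6-12 and 357 aged 13-17. Both bands are large enough to carry a joint model.

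**Possible overlap with age.** The shares above 30 are assumptions, applied to 524 and 536:

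| Assumed share above 30 (6-12 / 13-17) | Above 30, aged 6-12 | Above 30, aged 13-17 | Adolescent share of group above 30 |
|---|---|---|---|
| 15% / 15% | 79 | 80 | 51% |
| 10% / 20% | 52 | 107 | 67% |
| 5% / 20% | 26 | 107 | 80% |
| 2% / 30% | 10 | 161 | 94% |

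The first row shows no association with age. In the last row the group above 30 is almost entirely adolescent. The documents do not say which row is closest.

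**Size of a percentile-defined group.** At the 15% of section 5, and an assumed upper value of 30% because section 2.2 links obesity to elevated BP:

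- Aim 2: 0.15 × 706 = 106 to 0.30 × 706 = 212.
- Aim 1 (4,840 patients in section 8.2): 0.15 × 4,840 = 726 to 0.30 × 4,840 = 1,452.

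These are sizes of the replacement group. They do not measure the mismatch or the overlap.

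**The case against.** The strongest reply has four parts.

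- **Overlap with age is not shown.** This stands. The documents contain no BMI-by-age data, and the scenarios above run from no association to near-complete overlap. The overlap can be put only as a conditional.
- **The CDS gives little reason to cut at the 95th percentile.** This largely stands. A reader might infer that, because the CDS reacts to that percentile, effects must be expected to differ there. But section 6.1.1 only adds a note on obesity, and the tailored recommendations follow the level and persistence of BP. Section 4.1.2 separates the two strategies by training, feedback and incentives, not CDS logic, so the note is common to both arms. The case for the percentile rests on the protocol's own definition of obesity and its Aim 2 covariate.
- **The protocol does not use percentiles throughout.** True. Appendix 1 refers to BMI without a percentile, and the Aim 1 model has no BMI covariate. But wherever the protocol defines obesity, it does so by percentile.
- **Joint fitting may already be intended.** The wording on interaction terms allows it but does not promise it, so this is an ambiguity.

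None of this removes the mismatch between the subgroup cut and the protocol's definition of obesity, or supplies a reason for it.

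**Conclusion.** The point holds as a minor one. The split at 30 does not identify the protocol's obese group, leaves one value unassigned and changes scale without explanation. This follows from the text alone. Partial confounding with the age subgroup follows only if absolute BMI rises with age in this population, and its extent cannot be computed.

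Two stronger readings are not supported. A reader might infer that the protocol defines obesity in two conflicting ways, but section 8.4.1 never calls the group above 30 obese. A reader might also infer that the trial's conclusions are at risk. They are not: H1 to H4, alpha and power do not depend on this cut, and arm contrasts within a BMI group are not biased by where it is placed. What is affected is the interpretation of a secondary analysis that the plan itself makes conditional on feasibility.

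**What to change.** In section 8.4.1, define the subgroup as BMI at or above versus below the 95th percentile at the index visit, using the percentile the CDS already calculates. Every value is then assigned. State that the age-by-arm and BMI-by-arm terms are fitted in the same model, since a percentile cut may not remove all overlap with age.

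Date the change before subgroup results are examined. Section 4.1.3 allows analysis as data arrive, so this may no longer be possible. If results have been seen, keep the split at 30, assign exactly 30 to one side, and report the percentile split beside it, labelled as added later.

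The cost is one phrase, one extra interaction term and a dated note, with no new data. The downside is a documented change or addition to a pre-specified subgroup.

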9 SUPPORTING DOCUMENTATION AND OPERATIONAL CONSIDERATIONS

9.1 REGULATORY, ETHICAL, AND STUDY OVERSIGHT CONSIDERATIONS

9.1.1 INFORMED CONSENT PROCESS

We are requesting a waiver of informed consent of providers and rooming staff, and a waiver of parental permission and child assent of patients, to implement and operate the PedsBP CDS in primary care clinics for the following reasons: (a) All treatment options included in the CDS algorithms are based on current national guidelines, and no other care

recommendations are provided. Thus, the care recommendations provided conform to current standards of care and ought not to represent any risk to patients beyond the routine risk that all patients assume whenever they have contact with the medical care system. (b) At intervention clinic training sessions and on CDS displays in the EHR, we emphasize that the material provided is meant only as a suggestion, not as a mandate, and that it is inappropriate for a provider to follow suggested treatment options without further checking the clinical status of a given patient. (c) It would be impractical to consent or assent patients (due to large numbers) and impossible to answer the primary research questions (due to selection effects related to consent) if informed consent of patients were required.

Because use of PedsBP CDS tool itself is considered usual care and all necessary data to determine eligibility, implement and operate the PedsBP CDS intervention, test the study hypotheses and assess the impact of the intervention are derived from electronic health records (EHRs), waivers of HIPAA authorization, informed consent, parental permission and child assent are being requested to identify and enroll patients who are to be included in the study.

All rooming staff and PCPs will be consented to participate in any interviews or surveys. **DETAILS OF INTERVIEWS AND SURVEYS ARE PROVIDED IN SEPARATE PROTOCOLS.**

9.1.1.1 SURVEY AND INTERVIEW CONSENT PROCEDURES AND DOCUMENTATION

DETAILS OF INTERVIEWS AND SURVEYS ARE PROVIDED IN SEPARATE PROTOCOLS.

The informed consent process is a means of providing study information to each prospective participant and allows for an informed decision about participation in the study. The informed consent forms will include all the required elements of informed consent. Prior to informed consent, research staff will provide a detailed description of the study and interview or survey to the potential participant and provide a copy of the consent to read. If the participant is interested in participating in the interview or survey, he or she will have the opportunity to ask any questions related to participation.

The informed consent forms will be updated or revised whenever important new safety information is available or whenever the protocol is amended in a way that may affect participants' participation in the study. Participants will be informed that their participation is voluntary and they may withdraw from the study at any time, for any reason, without penalty. Individuals who refuse to participate in interviews or surveys or who withdraw will be treated without prejudice.

9.1.3 SAFETY OVERSIGHT

The PIs, Drs. [name] and [name] will be responsible for the safety of the trial and adherence with the study protocol. In addition, we have invited a single medical monitor, independent of the study, [name], to lead the Data Safety Monitoring Plan. As in prior work by our group, we will select an independent medical monitor with relevant clinical and research expertise. The intervention provides point-of-care clinical decision support (CDS) to primary care providers designed to identify children and adolescents with elevated BP and HTN and suggests care options that may be appropriate in specific clinical scenarios. Suggestions provided to PCPs are based on national recommendations and will be further vetted by clinical leaders at Essentia Health (EH) prior to implementation. Alerts are designed to support clinicians' decision making, not to override clinical judgment.

The study team will convene within 3 months of the beginning of the intervention at a face-to-face or phone meeting with the independent safety monitor and will meet up to twice annually through the study. The independent safety monitor will provide guidance on the study evaluation and intervention protocols, including quality assurance and safety issues related to the intervention protocols, implementation strategies, and data-handling activities. The independent safety monitor will also provide periodic input and feedback on the progress of study accrual of patients, eligibility determination issues, data completion rates, and adverse events. Consistent with NIH, AHRQ, EH and HealthPartners (HP) policy, the medical monitor is not be affiliated with HP or with EH.

As a minimal risk, pragmatic trial, we do not propose interim analyses or stopping rules. A special focus of interest will be the safety of patients exposed to the study intervention. We will collect data from the electronic health record (EHR) or the CDS to identify potential rare adverse events related to untreated or undertreated HTN, such as malignant HTN or stroke. In addition, using automated methods we will monitor for hospitalizations within 6 months following exposure to the CDS, with additional clinical review regarding any potential for the CDS to have impacted subsequent events. The PIs will be responsible for responding to unsolicited complaints, for reviewing potential serious adverse events, and for additional communications with the IRB and with AHRQ.

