1.1 SYNOPSIS

Title:	Improving Recognition and Management of Hypertension in Youth: Comparing Approaches for Extending Effective CDS for use in a Large Rural Health System
Grant Number:	AHRQ 1R18HS027402-01A1
Study Description:	This research project will adapt the PedsBP clinical decision support (CDS) tool for use at Essentia Health and measure the implementation processes and outcomes. This minimal risk, pragmatic trial will randomize up to 45 Essentia clinics in a 3-arm, cluster-randomized trial. Clinics will be randomly allocated in a 1:1:1 allocation ratio to usual care, low-intensity implementation, or high-intensity implementation of the PedsBP CDS. Study-eligible patients will be allocated to the study arm assigned to the clinic at which the patient has an index visit when blood pressure (BP) is measured. Clinic providers and rooming staff will be interviewed and surveyed to assess experience and satisfaction with the CDS.
Objectives:	Identify optimal intervention implementation strategies for the PedsBP CDS tool. Post-implementation comparisons of high- plus low-intensity implementation versus usual care and high- versus low-intensity implementation will be conducted for the primary endpoints of BP remeasurement at the index visit (for patients with an elevated first BP), and BP recognition within 6 months of the index visit (for patients newly meeting HTN criteria).
Endpoints:	There are two primary outcomes. One is repeat BP measurement during the same clinic visit, of an initial BP that is \geq 95th percentile for children 6-12 years or \geq 130/80 mmHg for adolescents 13-17 years. Repeat BPs can be measured by providers or rooming staff but will only contribute to this outcome if recorded in the vitals section of the EHR. The other primary outcome is clinical recognition of HTN within 6 months of meeting criteria for HTN. Clinical recognition will include a new diagnosis of HTN (ICD-10: I10) or elevated BP (ICD-10: R03), adding HTN or elevated BP to the problem list. Secondary outcomes will describe management within 6 months of meeting criteria for HTN including: lifestyle counseling, dietitian referrals, subspecialty referrals, initiation of antihypertensive medications and receipt of diagnostic imaging (echocardiogram or renal ultrasound). BP control at 12 months following the index date meeting criteria for HTN will be an exploratory outcome.

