8.3 POPULATIONS FOR ANALYSES

We will continue to engage with EH leadership to ensure the active participation of EH clinics. EH leadership support for this project, as evidenced in the letters of support, ensures the participation of primary care clinics.

Patients 6 to 17 years of age with a BP recorded at a participating EH primary care clinic will be eligible and automatically enrolled on the basis of data recorded in the EHR and captured by the PedsBP CDS. Given that one of the primary purposes of the study is to test the effectiveness of the different intervention approaches, including a high-intensity intervention with additional outreach and engagement of clinicians and rooming staff, we do not plan to conduct additional recruitment or retention activities.

Aim 1 outcomes will be assessed in the context of care provided at the index visit with an isolated hypertensive BP recorded. Aim 2 outcomes will be assessed over a period of 6 months following when a patient meets criteria for HTN. Clinical recognition of HTN, dietitian or other lifestyle referral and lifestyle counseling will be assessed based on care received. There will be no additional efforts to recall patients for additional study visits. For subjects with no follow-up visits, Aim 2 outcomes will be assessed based on clinical actions at the index visit.

Providers and rooming staff will be invited to participate in surveys and in-depth interviews through email or in-person recruitment by EH study staff. Surveys and interviews will be conducted at the time of recruitment as well as through a follow-up survey at the end of the intervention period. We will work with clinic administrative staff as necessary to help coordinate interviews and surveys with clinicians and rooming staff in a way that is not disruptive to regular clinic operations.

Data sources

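### As written, the protocol counts hospitalisations only after CDS exposure and states no usual-care or reference rate, so the safety review could not tell an excess from background.

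*Combined protocol and SAP*

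**What the plan says.** All references are to the combined protocol and SAP.

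- **Section 9.1.3 (Safety oversight), hospitalisations.** The plan is that "using automated methods we will monitor for hospitalizations within 6 months following exposure to the CDS".
- **Section 9.1.3, how events are judged.** The hospitalisations found in this way are then assessed one by one, "with additional clinical review regarding any potential for the CDS to have impacted subsequent events".
- **Section 9.1.3, focus.** "A special focus of interest will be the safety of patients exposed to the study intervention".
- **Section 9.1.3, named events.** EHR or CDS data will also be used to "identify potential rare adverse events related to untreated or undertreated HTN, such as malignant HTN or stroke". That sentence is not limited to any arm.
- **Section 9.1.3, interim looks.** "we do not propose interim analyses or stopping rules".
- **Section 1.1 (Synopsis).** "Clinics will be randomly allocated in a 1:1:1 allocation ratio to usual care, low-intensity implementation, or high-intensity implementation of the PedsBP CDS". A concurrent randomised comparator therefore exists.
- **Section 8.3 (Populations for analyses).** Patients at participating clinics are "automatically enrolled on the basis of data recorded in the EHR and captured by the PedsBP CDS". The data-sources text in that section assigns a study ID at the index visit, defined as the first visit in the intervention period. It stores later encounters for eligible patients without restriction by arm.
- **Section 9.1.5.1 (Data collection and management).** Among encounter types, variable definitions are planned for outpatient encounters. Inpatient stays are not named.
- **Section 9.3 (Amendment history).** Amendment 7.0 added a data dictionary for safety and reporting. It is not among the documents reviewed.

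**The concern.** The hospitalisation window opens at exposure to the CDS. On the natural reading, usual-care patients have no such date and are not followed for this event. The output is then one count, from the two CDS arms, judged case by case by people who know that every patient had the CDS.

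That process can answer whether the CDS plausibly contributed to a particular admission. It cannot answer whether there were more admissions than there would otherwise have been. With no interim analysis or stopping rule, this monitoring is a main source of safety evidence in the trial. Section 9.1.6 foresees switching the CDS on at all pediatric and family practice sites once the intervention period ends. The concurrent randomised comparison is cleanest before that happens.

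**Working it through.** **1. Is there a plan figure to reproduce?** No. The documents give no hospitalisation rate, no ICC for hospitalisation, no safety threshold and no safety power. The rates and ICCs below are assumptions and serve only as illustration.

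**2. Arm sizes.** Section 8.2 reports that "there were 44,061 unique patients age 6-17 with visits to the 45 largest EH primary care clinics in an 18-month period". With 1:1:1 allocation and clinics of equal size:

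- CDS arms: 44,061 × 2/3 = 29,374
- Usual care: 44,061 / 3 = 14,687
- Mean per clinic: 44,061 / 45 = 979

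For the 7,258 patients with an elevated first BP (section 8.2), the same split gives 4,839 and 2,419, about 161 per clinic.

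**3. Why a one-arm count is not enough.** Suppose 294 patients in the CDS arms are hospitalised.

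- Background 1%, no effect: 29,374 × 0.01 = 294
- Background 0.5%, doubled: 29,374 × 0.005 × 2 = 294

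Nothing in the documents separates these two cases.

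**4. What a usual-care count would add.** Let e1 and e2 be the expected events with no effect, and DE = 1 + (m − 1) × ICC the design effect for m patients per clinic. For two-sided alpha 0.05 and 80% power:

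Detectable ratio = exp(2.80 × sqrt(DE × (1/e1 + 1/e2)))

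All patients, 1% rate, e1 = 294, e2 = 147, sqrt(1/e1 + 1/e2) = 0.101:

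- ICC 0, DE 1.00: exp(2.80 × 0.101) = 1.33
- ICC 0.001, DE 1.98: 1.49
- ICC 0.005, DE 5.89: 1.99

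Elevated first BP only, 1% rate, e1 = 48.4, e2 = 24.2, sqrt(1/e1 + 1/e2) = 0.249:

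- ICC 0: exp(2.80 × 0.249) = 2.01
- ICC 0.001, DE 1.16: 2.12
- ICC 0.005, DE 1.80: 2.55

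**5. Cross-check by a second method.** Solving a two-proportion power function at 80% with the same design effects gives somewhat smaller ratios at a 1% rate:

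| Population | ICC 0 | ICC 0.001 | ICC 0.005 |
|---|---|---|---|
| All 44,061 | 1.30 | 1.44 | 1.83 |
| 7,258 with elevated first BP | 1.84 | 1.92 | 2.20 |

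By this method, across assumed rates of 0.5% to 3% and ICCs of 0 to 0.005, the detectable ratio runs from 1.17 to 2.27 for all patients and from 1.44 to 2.89 for those with an elevated first BP. For the 1,060 expected to newly meet HTN criteria (707 against 353), it runs from 2.36 to 6.38.

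**6. Direction of the remaining error.** Clinic volume over 18 months ranges from 145 to 6,556 (section 6.2). Unequal clinic sizes would worsen all the clustered figures.

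**The case against.** **The comparison may be defined elsewhere.** Section 9.1.3 refers to a Data Safety Monitoring Plan, and section 9.3 to a safety data dictionary. Tabulation by arm could be in either. This stands: the point is that the protocol does not state a comparison, and it would be wrong to infer that none exists.

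**Exposure is not defined.** Section 6.1.1 activates the CDS in a randomised study clinic, and usual-care clinics are randomised. Appendix 1 takes web-service data from index visits at any randomised clinic. The service may therefore run unseen in usual care. This lowers certainty. However, section 9.1.3 speaks of patients exposed to the study intervention, which does not naturally include usual care.

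**The protocol promises only case review.** It makes no claim of no excess harm, and focusing on exposed patients is deliberate. This is fair, and case review by an independent monitor has real value. It still leaves the rate question unanswered when the comparator is at hand.

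**A comparator would not detect a modest excess.** A reader might take the unclustered 1.33 as the sensitivity gained. The working does not support that. Clustering raises it to about 1.5 or 2.0. The repeat-BP prompt and tailored advice fire only at an elevated BP, so any effect would be diluted in the full population.

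**The named events are not restricted.** A reader might infer that malignant HTN and stroke are also tracked only in CDS clinics. The text does not say so; only the hospitalisation sentence is tied to exposure.

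**Conclusion.** The point holds as a gap in the stated plan. Followed as written, section 9.1.3 yields a count of hospitalisations after CDS exposure with no reference rate, and such a count cannot separate an excess from background.

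It does not follow that safety monitoring is absent, that individual harms would be missed, or that usual-care data cannot be obtained. The index visit is an anchor shared by all three arms, and later encounters are stored for eligible patients in any arm.

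The gain from a comparator is real but limited: at an assumed 1% rate, only ratios of about 1.3 to 2.0 or larger could be seen among all patients, and about 2 or larger among those with an elevated first BP. These figures rest on assumed rates and ICCs and on equal clinic sizes. Severity is modest, because the trial is described as minimal risk and no primary or secondary efficacy analysis depends on this.

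**What to change.** Amend section 9.1.3, or cite the safety data dictionary or monitoring plan if it already covers this:

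1. Run the same automated hospitalisation query in all three arms, for 6 months from the index visit (first visit in the intervention period).
2. Give the independent monitor counts, denominators and rates by arm, with a rate ratio and confidence interval that allow for clinic clustering. Do this for all patients and for those with an elevated first BP.
3. Report the malignant HTN and stroke events, already to be collected, by arm as well.
4. Define exposure to the CDS. State whether patients with known hypertension, who receive alerts but are left out of the efficacy analyses (section 2.3.4), are in the denominators.
5. State in advance that precision is limited, so that a ratio near 1 with a wide interval is not read as proof of no harm.

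Cost: some extra programming, including a definition of an inpatient encounter, since section 9.1.5.1 names only outpatient encounters. The documents do not describe the existing query, so the effort cannot be sized from them. Usual-care events would need rates only, without added clinical review. No clinical rule changes.
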